In the case of remote approach by phone, a study team member will attempt to contact the patient 3 times. If the patient contact cannot be established, the study team member will email a copy of the recruitment letter to the patient (Appendix AC). The recruitment letter encourages the patient to reach out to the study staff if they are interested in participating. If a patient reaches out to the study staff then the study letter, consent form, and HIPAA authorization form (Appendix W) will be reviewed before the patient provides written consent. During remote approaches by phone the study letter, consent and HIPAA forms will be sent by email through a secure and personalized link in REDCap. While discussing the study letter and consent the study staff will emphasize that participation is voluntary and the participant may stop participating at any time. Consent discussions may take place over the phone or HIPAA-compliant Zoom.

Protection against physical risks: The study team has placed extensive protections against the aforementioned physical risks of the app which have been approved in the initial app protocol (DF/HCC #18-504). These protections significantly exceed the level of support and guidance that patients would receive with usual care. Finally, the patient-facing app always instructs patients to contact their care teams and reminds them that the research portal is not monitored continuously.

The STAMP+CBT application sets a low bar for instructing patients to contact their care teams for reported symptoms. This includes reporting any new pain, fever, new or worsening back pain, new or worsening chest pain, any pain rated ≥ 8 out of a 0 to 10 scale (See table 3 for the detailed list). Moreover, if patients report moderate to severe pain levels that do not meet the previous criteria, in addition to receiving education about their pain management, they are also reminded that their care team wants to hear from them if they are concerned about their symptoms or if their symptoms are not improving. A link to their care team's number is included in the application. This level of support is much greater than what patients have usually with routine care.

Participants may feel reassured that their symptoms are being monitored and be less likely to call their care team. We have sought to mitigate this possibility in multiple ways. First, study staff emphasize and reiterate that the study platform is not monitored continuously during onboarding. Staff tell participants to contact their care team or call 911 should any concerning symptoms arise. Second, when patients report potentially serious symptoms, they are specifically instructed by the application to notify their care team by calling or paging after hours (the clinic number is included in the application). See Table 3 for the list of symptoms that prompts phone contact.

Protection against psychological risks: If in the course of their participation patients raise significant emotional distress, the appropriate care team members (i.e. nurse navigator, physician, mid-level provider) will be contacted to make appropriate social work or mental health referrals. Similar to that of physical

risks, this app provides closer monitoring than what is provided for usual care for psychosocial needs.

Benefits and knowledge to be gained: Using the STAMP+CBT app and taking part in this research study may or may not benefit participants. We hope that by reviewing the content in the STAMP+CBT app, patients are able to better manage their symptoms and the increased flow of information between a patient and their care team improves their experiences. We also hope the information learned from this research study will provide more information about how patients' pain management experience varies between clinic visits, as at-home app management will allow for increased monitoring of system and therefore increased access to daily symptom data. Lastly, we hope this will help patients and their care team work together during and between visits to achieve better symptom management in cancer patients.

L. Statistical Methods

Statistical analyses will be utilized in this pilot intervention to ascertain feasibility and acceptability of the STAMP+CBT app. We will measure time spent on the app per day and per week, completion rates for surveys and content review, and frequency of app interactions over the course of the pilot. Defined using precision analysis, we will consider the intervention to be **feasible** if $\geq 70\%$ of subjects complete any activity on the app at least 50% of days on study. The intervention will be considered **acceptable** if $>80\%$ of the sample rate the app as satisfactory and useful (4 or higher/5); lower ratings will lead to app and content refinements. Other feasibility measures will assess time to accrual participation rates, and study retention and completion rates. Other acceptability outcomes will be assessed through qualitative debriefing interviews with patients evaluating the perceived benefits, usefulness, and satisfaction of the app, and quantitative acceptability ratings of the app's functionality, perceived utility, ease of use, and content relevance. **Power calculation:** With 35 evaluable patients, we will be able to estimate these proportions with margins of error (half of a 95% confidence interval) of approximately 18% or less assuming that the feasibility threshold of 70% is reached. This margin of error is small enough so that proportion estimates relevant to study feasibility will be accurate and provide informative guidance for future, larger studies. Although power is not sufficient in this pilot, we will explore associations between levels of engagement and changes in pain severity/interference, opioid use, catastrophizing, sleep, mood, and pain self-efficacy.

Because interviews produce qualitative results, statistical analyses will not be employed for a portion of this study. The study team will review qualitative feedback from patients and find common themes related to app feasibility and acceptability. The study team will use the common themes derived from qualitative thematic analysis of the interview that review this feasibility study to guide further iterations of the application and study procedures for future larger, efficacy study of the STAMP+CBT app.

M. Data and Safety Monitoring Plan

SCC Clinical Trials Office (CTO) study coordinators will assist in pre-screening, recruiting, and consenting patients. Once patients have consented, the principal investigator's study team will complete app onboarding and study procedures, except completing documentation on clinicaltrials.gov.

For this study, we will utilize the SCC CTO for registering human subjects for trials via the clinical staff, including registration in Oncore; ensuring high-quality standards are used for data collection; ongoing management of clinical trials, auditing, and data and safety monitoring; and coordinating quality assurance efforts related to clinical research.

The following Data and Safety Monitoring Plan (DSMP) will ensure that our OU/SCC project will comply with Federal Regulations, Health Insurance Portability and Accountability Act (HIPAA) requirements, and applicable OU/SCC Guidelines.

The OU/SCC will:

- Ensure that the investigators and study team members are qualified and appropriately resourced to conduct the protocol.
- Ensure that each participating investigator and study team member receives adequate protocol training prior to enrolling participants and throughout trial's conduct as needed. The Principal Investigator will ultimately be responsible to make sure that required personnel have completed their training.
- Monitor progress and overall conduct of the study by [name] team.
- Ensure all OU Institutional Review Board (IRB), OU/SCC and other applicable reporting requirements are met.
- Review data and maintain timely submission of data for study analysis.
- Ensure compliance with all requirements as set forth in the Code of Federal Regulations, applicable OU/SCC requirements, HIPAA requirements, and the approved protocol.
- Commit to the provision that the protocol will not be rewritten or modified by anyone other than the OU/SCC Sponsor.
- Monitor accrual and address problems meeting accrual requirements.
- Maintain documentation of Adverse Event reports and deviations/violation the OU/SCC study team for timely review.
- Maintain Regulatory documents which includes: IRB approvals/notifications, AE submissions, IRB approved consents.

Patient Registration: To register a participant, we will send the study letter with signed informed consent document/ HIPAA authorization form (if separate from the informed consent document) and eligibility checklist to SCC Clinical Trials Office. At the time of registration, SCC Clinical Trials Office requires the following identifiers for all subjects: initials, date of birth, gender, race and ethnicity. Once eligibility has been established and the participant successfully registered, the participant is assigned a unique protocol case number that will be used on all de-identified subsequent communication and documents. Participation may not begin without confirmation from the Coordinating Center that the participant has been registered.

Safety Monitoring:

The study and all research activities will be monitored by the study team and the PI. The PI and project manager will work closely with SCC Clinical Trials Office to implement the Data and Safety Monitoring Plan that is consistent with SCC Clinical Trials Office. All members of the research team will be responsible for immediately reporting breaches to confidentiality or data security, or adverse reactions, to the PI, and the study tracking database will provide tools for tracking and reporting any of these issues.

The PI and project manager will be responsible for timely submission of any necessary reports of adverse events, revisions to the protocol that indicate a change in risk for participants, or actions taken by the IRBs regarding the research. The project manager will be responsible for submission of the final approved protocol and any subsequent amended protocols to the OUHSC IRB. The CTO regulatory team will maintain a copy of the master regulatory binder in eREG, documenting IRB approved versions of the study protocol and consent forms for, correspondence with the IRB, and general human subjects and study-specific staff training.

The PI will monitor participant accrual monthly. A data submission and processing timeline will be developed for each data element. The PI and the project manager will monitor data submission and processing monthly.

The PI will be responsible for assessing external factors or relevant information (e.g., developments in the literature) that may impact the safety or participants or ethics of the research study.

It is unlikely that the intervention will cause any clinically significant AE's, as the intervention is predominantly a system by which patients can self-report symptoms, and receive education/coaching around symptom self-management. All adverse events will be reported to the OUHSC IRB and study investigators in accordance with usual procedure. Any serious adverse event (SAE), defined as an adverse event that results in death, is life threatening, results in hospitalization, or results in another important medical event, will be reported to the IRB and to the study investigators within 2 working days of occurrence.

Although a DSMB is not required for this small pilot study of a behavioral intervention, any SAE's related to study participation will be immediately reported to the PI and study team ([name]). All SAE's will be reviewed by the study staff within 2 working days of occurrence. All SAEs will also be reported to the NIH within 5 business days. The NIH will not be directly involved in the review of these SAEs, but they will be notified to maintain transparency during the trial. If the SAE's are determined to be likely related to the intervention, the protocol and consent forms will be amended as necessary.

Data Management: PHI data will be collected using REDCap and the STAMP+CBT app.

REDCap: For this study, data will be collected using the REDCap platform. REDCap (Research Electronic Data Capture) is a free, secure, HIPAA-compliant web-based application. Data collection is customized for each study or clinical trial by the research team with guidance from REDCap administrators. REDCap is built around HIPAA guidelines and is 21 CFR Part 11 capable.

STAMP+CBT app: The final application will be HIPAA compliant and compliant with OU security and privacy standards through the Insight app platform developed at the OUHSC/HPRC.

Study specific procedure to maximize data security:

Controlled access: The REDCap and STAMP+CBT app administrators will set up all user accounts so that each user only has access to their own relevant participant data in a prototype model only.

Use of unique study ID numbers: REDCap automatically assigns unique study ID numbers to each new case.

Extensive training: All personnel involved in this study are required to complete and document completion of extensive protocol training. Furthermore, all research personnel are required to have valid certification of human subjects research training.

Storage of Patient Research Data: All patient research data is subject to HIPAA regulations at the host institution.

Note: Interviews will be audio and video recorded using the HIPAA-compliant platform, Zoom. The recordings will be stored in a password protected dropbox business account and destroyed once the data analysis is complete. The audio recordings will be transcribed analysis of feedback. The entire interview will not be conducted in a group setting. It is important to keep the facial features of patients in the videos as this provides important sociobehavioral analysis.

The staff at University of Oklahoma will be responsible for monitoring the data for completion, accuracy, and compliance. All personnel involved in this study are required to complete and document completion of extensive protocol training.

Furthermore, all research personnel are required to have valid certification of human subjects' research training.

N. Data Sharing

As noted elsewhere, data collection for this project will take place at the TSET Health Promotion Research Center, Stephenson Cancer Center at the University of Oklahoma Health Sciences Center.

De-identified data will be shared with co-investigators at Dana-Farber Cancer Institute and Brigham and Women's Hospital in Boston, MA.

O. Confidentiality

Protection against privacy risks: To monitor the risk of loss of confidentiality/privacy, the study team has ensured that the STAMP+CBT app is HIPAA compliant and meet the privacy and security standards set by University of Oklahoma Health Sciences Center. In addition, all collected study data will be maintained in a secure location and personal identifiers will be removed.

To maximize data security, both REDCap and STAMP+CBT employ:

- User Privileges - To ensure that users have access only to data and information that they are supposed to have within the application, user privileges are utilized within the software. Each user has their own account, and their user account will only have access to information that they themselves have created or to which administrators have granted them access.
- Password-protection & Authentication - Both systems are password protected and implement authentication to validate the identity of end-users that log in to the system.
- Logging and Audit Trail - Both systems maintain built-in audit trails that log all user activity and all pages viewed by every user.

Literature Cited

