The purpose of this study is to pilot test a novel mHealth intervention that harmonizes psychological and pharmacological support for advanced cancer pain. I adapted core components of pain-CBT and integrated them into STAMP (Smartphone Technology to Alleviate Malignant Pain), an existing NINR-funded cancer pain mHealth intervention. STAMP enables patients with advanced cancer to track their pain, opioid use, and side effects (R21 NR017745, PI, [name]; IRB #18-504 at Dana Farber Cancer Institute). It delivers tailored education and self-management advice while facilitating clinician monitoring and patients' proactive outreach. We developed an extensive suite of multi-media cancer pain psycho-education covering core pain psychology principles. We refined and integrated pain-CBT treatment with medically oriented self-management support in STAMP (OUHSC IRB #13-725). Capitalizing on mHealth technology, this app strives to destigmatize pain psychology through a potentially scalable model that disseminates behavioral treatments for advanced cancer pain paired with their palliative care pain management plan.

Aim 1 (App Feasibility and Acceptability): Determine feasibility and acceptability of the STAMP+CBT app: up to 60 patients with advanced cancer pain will be recruited from Stephenson Cancer Center outpatient supportive care clinics at a major cancer center to participate in a single-arm, 6-week study of STAMP+CBT (4-week intervention period and a 2-week post intervention period). Surveys at baseline, 4 weeks (end of intervention period), and 6 weeks (end of 2-week post intervention period) will explore trends in pain specific intensity, self-efficacy, and catastrophizing, physical function, opioid use, and quality of life. End-of-study interviews with up to 30 patients will identify facilitators and barriers to usability, acceptability, and satisfaction of the app. The primary outcome will be feasibility evaluating 1) app retention rates and 2) completion of app exercises.

Outcomes and accomplishments

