We have completed initial user acceptability testing of the app with patients from our target population (n=6) at the SCC (OUHSC IRB # 13-725) testing the app at home for 2-4 weeks. We are also currently completing pilot testing of the app with patients with advanced cancer at the DFCI in Boston, MA (DFCI IRB #21-719). Study procedures outlined in this protocol parallel those approved in DFCI IRB #21-719 protocol (currently enrolling). At this time, 5 patients have been enrolled in the study, we are recruiting 10 more patients to complete testing of the app at home for 4 weeks, in addition to completing survey assessments – similar to those outlined in this protocol. Patients who have tested the app to date (DFCI pilot, n=3; SCC pre-pilot, n=5) have reported finding the app easy to use (5-Point Likert scale for all items: DFCI=4.33; SCC=4.80), understandable (DFCI=5; SCC=4.8), and enjoyable (DFCI=4.33; SCC=3.80). They reported feeling that it took an appropriate amount of time to use the app (DFCI=4.33; SCC=4.20) and were satisfied with the app overall (DFCI=4.33; SCC=4.60). Patients at DFCI who tested the app for 4 weeks took an average of 57.14% of the surveys pushed by the app (median=62.50%). Patients at SCC who had tested the app for 2 weeks took an average of 54.76% of surveys pushed to them (median=64.29%). **This specific study outlined in this protocol will enable pilot testing of the application in Oklahoma, allowing for comparison between patient samples between Boston and Oklahoma.**

D. Research Design and Methods (What, When, How, Where)

STUDY PROCEDURES:

Patients in the Pilot Cohort will pilot the application for 4 weeks (4-week intervention period) and remain on study through the 2-week post-intervention period (6-weeks on study total). The onboarding and monitoring protocol are available in Appendix S. A study team member will contact participants after 4 weeks (end of intervention period), and 6 weeks (end of 2-week post-intervention period). The purpose of these contacts would be to schedule the end of intervention interview and confirm completion of survey assessments (end of 4-week intervention period), as well as the final survey assessments at 6 weeks (end of 2-week post intervention period).

Participants will fall into only one eligibility category:

Table 1: Brief description of pilot cohort activities

Description	Components of Participation

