The Baseline survey will assess socio-demographics, baseline technology use, current comorbidities, current pain management, pain severity, opioid use, pain and psychological symptoms, and quality of life, with metrics shown in Table 4. The end of 4-week intervention period survey will largely replicate the baseline survey; additionally, patients will rate their satisfaction with STAMP+CBT using the 6-item Acceptability E-scale. Surveys will be used to assess pain and psychological symptom trajectory, medication use, and quality of life. See **Appendix P** for the Baseline survey items, **Appendix Q** for 4-week (end of 4-week intervention period) survey items, and **Appendix R** for 2-week (post intervention period) follow-up survey items. Additionally, a subset of patients (up to 15) will be invited for a qualitative interview focused on study burden, facilitators/barriers to app use, satisfaction, and perceived utility in order to guide future refinements to the app (see Appendix T) when they complete use of the app at 4 weeks (end of intervention study period).

Intervention

After the patient completes the baseline survey, a study team member will meet with the patient (in person or virtually), to assist in either 1) downloading the application onto participants' mobile device or 2) providing/mailing the study phone to the participant. The study team member will help to register the patient to the app and help set up any preferences. The study team member will then conduct a 20-30 minute tutorial on the STAMP+CBT app and its intended use (Appendix S). The study team member will also input the patient's pain medications from the EMR, reconciling this list with the patient. The participant will also input their desired goal to work towards for the duration of the trial. During the trial, there is also a survey item that if selected notifies the research team whether a patients' medication or goal needs to be changed and reflected in the app.

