Identifying potential subjects: Potentially eligible patients will be identified by 1) referrals from clinic staff, and 2) by pre-screening the EMR for outpatient solid tumor, hematology disease center clinics, or the supportive care clinic schedules. Once the study team identifies a potentially eligible patient, the team will reach out to the treating clinician for permission to approach and offer engagement in the study. If the provider does not approve that the study staff approach a patient, the study staff will NOT approach the patient to offer engagement in the study. Patients will provide written consent on the consent form and HIPAA forms after reviewing the consent and HIPAA forms with a study staff member according to IRB procedures (see Appendices AD, X, and Y).

Recruitment of potential subjects: Under a HIPAA waiver, study staff will look in the electronic medical record, scheduling systems, and inpatient lists to pre-screen and identify potentially eligible patients who meet the eligibility criteria. Study staff may also accept potential patient referrals from site clinicians.

Purposive sampling based on data from the electronic medical record (e.g., demographics, cancer stage, number of recent hospitalizations, number of prescription drugs) will be used to ensure that perspectives of diverse patients are included.

Patient approaches can occur through the following mechanisms dependent upon COVID-19 related research regulations and clinic operations at the time.

- In person approach: A study team member will approach the patient in clinic to explain the study and offer participation. Interested participants will then review the study letter, consent and HIPAA forms with a research team member (Appendices AD, W, and X) and if interested provide signed consent. The patient and a study team member will then set up a time to onboard to the application.

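### The only interview on barriers to app use comes at the end of the 4-week app period: early stoppers are not provided for, and low users are included only by chance

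*Combined protocol and SAP*

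**What the plan says.** Section D (Survey Assessments) states that "a subset of patients (up to 15) will be invited". It describes what they are asked to do as a "qualitative interview focused on study burden, facilitators/barriers to app use, satisfaction, and perceived utility", meant to inform later changes to the app. The invitation comes "when they complete use of the app at 4 weeks (end of intervention study period").

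The opening of Study Procedures, also in section D, ties the interview to the same time: "A study team member will contact participants after 4 weeks (end of intervention period), and 6 weeks", and "The purpose of these contacts would be to schedule the end of intervention interview" and to check that surveys are done. Table 1 lists it as an end-of-intervention interview. The Intervention text says patients will be invited and attaches no condition.

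Aim 1 in section A gives a different count and label: "End-of-study interviews with up to 30 patients will identify facilitators and barriers to usability, acceptability, and satisfaction of the app".

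Section J describes "Purposive sampling based on data from the electronic medical record", with demographics, stage, recent hospitalizations and number of prescription drugs as examples. Withdrawal of Subjects (section H) covers a missing baseline survey, early termination of the study and notice of withdrawal. It mentions neither an exit interview nor recording why a patient stopped.

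**The concern.** Engagement is the primary question. The app is called feasible if at least 70% of subjects are active on at least 50% of days on study (Endpoint 1 and section L). If that target is missed or only just met, patients who used the app little or gave it up are best placed to explain why.

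The interviews are meant to collect those explanations. Endpoint 1 combines qualitative and quantitative results for the feasibility and acceptability conclusion, and section L uses the interview themes to shape the app and the later efficacy study. Themes drawn mainly from patients who stayed would say less about why others did not.

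Little else in the plan fills the gap. Table 4 collects satisfaction and usability only at T2, the same week-4 point. The staff call within a week of enrollment is optional, is limited to technical or usability problems, and comes too early to capture later disengagement.

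**Working it through.** **1. What the text provides for each group**
- *Patients using the app to week 4:* contacted at week 4 and may be among the subset invited.
- *Low users still on study at week 4:* also contacted, with no minimum use stated. They may be invited, but no selection rule makes sure that any are.
- *Patients who stop the app but stay on study:* the week-4 contact could reach them, but nothing says the invitation covers them.
- *Patients who leave the study before week 4:* no interview is offered at any time.

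**2. The plan's own figure**

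The plan gives no figure for the make-up of the interview sample. Its only precision figure is a margin of about 18% or less with 35 evaluable patients at 70%. The simple normal-approximation value is 1.96 × √(0.70 × 0.30 / 35) = 0.152, or 15.2 points, which agrees with that statement. This point does not depend on it.

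**3. Share of interviews from low users**

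Inputs:
- Low-user share of 30%, the most that the 70% rule tolerates.
- 15 interviews (Survey Assessments).
- r, the likelihood that a low user is interviewed relative to other patients. The documents give no value, so r is an assumption shown over a range.

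Share = 0.30r / (0.30r + 0.70)

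| r | Share | Of 15 interviews |
|---|---|---|
| 1 | 0.300 / 1.000 = 30% | 4.5 |
| 1/2 | 0.150 / 0.850 = 17.6% | 2.6 |
| 1/3 | 0.100 / 0.800 = 12.5% | 1.9 |
| 1/4 | 0.075 / 0.775 = 9.7% | 1.5 |

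**4. The same question by reachability**

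With 35 patients the 70% rule needs 25 (0.70 × 35 = 24.5, rounded up), leaving at most 10 low users. Let R of these be reachable at week 4, again an assumption, and draw 15 interviewees at random from the 25 + R available. The expected number of low users is 15R / (25 + R), and the chance of none is C(25,15) / C(25+R,15).

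| R | Expected low users | Chance of none |
|---|---|---|
| 10 | 150/35 = 4.3 | 0.1% |
| 5 | 75/30 = 2.5 | 2% |
| 2 | 30/27 = 1.1 | 19% |
| 0 | 0 | 100% |

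**5. If 30 interviews are held, as in Aim 1**

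Among 35 patients with 25 at or above the threshold, 30 completed interviews must include at least 30 − 25 = 5 low users. Among 60 patients, 0.70 × 60 = 42 can be at or above it, so all 30 could come from that group.

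**The case against.** A reader might infer that the interview is restricted to completers and that low users are largely missed. The documents do not support this. The week-4 phrase can be read as a time point, the week-4 contact is with participants in general, and the Intervention text sets no use condition. A low user still on study can be invited. A large shortfall follows only if r or R is assumed to be small, and neither has a source in the text.

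A reader might also infer that the interviews alone decide how the app is changed. They do not. Low acceptability ratings also lead to refinements, and non-use itself is measured from app activity, retention and completion.

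Three further points deserve weight:
- The low-user label is unsettled. Patients use the app for 4 weeks (28 days) but are on study for 6 (42 days). If all 42 count, half is 21, and a patient active on 20 of 28 app days is labelled low. Such a patient is not obviously harder to interview.
- The count in Aim 1 weakens the chance element. It does not reach patients who have left.
- Appendix S (onboarding and monitoring), Appendix T (interview guide) and Appendix AD (consent form) are not in the text reviewed. Any of them might deal with interviewee selection or partial withdrawal.

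These arguments rule out the stronger readings. They leave standing that the protocol text specifies no interview for early stoppers and no selection by engagement.

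**Conclusion.** The concern holds in a limited form. The single barrier interview is placed at the end of the app period, early stoppers are not provided for, and inclusion of low users still on study is left to chance. Barrier themes may therefore lean toward patients who stayed.

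The size cannot be derived from the documents. With 30% low users and 15 interviews, the result runs from no shortfall (4.5) at equal likelihood down to about 1.5 at one quarter, and the assumed likelihood alone drives that range. The tables assume the boundary case of the 70% rule. The second also assumes random choice among reachable patients.

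The feasibility criterion, the evaluable sample of 35 and its margin of error are unaffected. This is an inexpensive improvement to the qualitative part of a pilot. Separately, the counts of up to 15 and up to 30 conflict, as may the end-of-intervention and end-of-study labels.

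**What to change.** Within the same interview total:
1. State how interviewees are chosen. Select across engagement levels, including patients below 50% of days, and say which days are counted. Staff already check engagement on the dashboard twice daily, Monday to Friday, so no new data are needed.
2. Offer the interview when a patient stops using the app, where the patient agrees to contact, and keep the week-4 invitation for the others.
3. Report the engagement of interviewed against non-interviewed patients, so that any remaining imbalance is visible.
4. Reconcile the interview number and timing between Aim 1 and Survey Assessments.

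The cost is a short protocol amendment with a working definition of stopping. Some stoppers will decline or be too ill, and section E already foresees deaths during the study. The imbalance would be reduced and reported, but not removed.
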